4.2 Premature discontinuation and missing data

If a patient is prematurely withdrawn from the study for any reason, the investigator must make every effort to perform the evaluations described for the D42 visit.

In the mITT set, missing values will be imputed using the last observation available on treatment method (LOCF).

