6.6.2 Early Study discontinuation

6.6.2.1 Criteria and modalities of premature end of treatment or subject exclusion from the study

The patient may voluntarily withdraw from the study at any time without penalty and for any reason without prejudice to her future medical care (Declaration of Helsinki).

The patient must be withdrawn from the study if, in the opinion of the investigator, there is any situation or condition which puts the patient at significant risk.

The investigator may decide to withdraw a patient for the following reasons:

- Adverse event(s) or Adverse Effect(s) necessitating study discontinuation ,
- Ocular dryness worsening from baseline according to the investigator's judgement and/or ocular examination

- Lack of efficacy: if the patient or the investigator does not feel that the treatment has adequately relieved his/her symptoms,
- Patient's request.
- Other reason.

In case of withdrawal from the study, the investigator will prescribe the best appropriate treatment to the patient.

In all cases, the date and the primary reason for withdrawal, must be recorded on the case report form (CRF) and patient files (source documentation).

If a patient is prematurely withdrawn from the study for any reason, the investigator must make every effort to perform the evaluations described for the Day 42 visit.

The patient discontinued for AE(s) will be followed-up after discontinuation until the event is resolved or considered medically stable by the investigator.

If a patient is lost-to-follow-up, the investigator must do his/her best to contact the patient initially by phone, then by letter, and finally by certified mail. If no response is obtained from the patient, the investigator is encouraged to contact one of the patient's relatives or her general physician. The evidence of these contacts must be recorded in the patient files.

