1.5 Sample size considerations

The primary efficacy criterion is the change from baseline in ocular symptoms at D42 assessed using a VAS. Assuming that the mean change is 12, the standard deviation (SD) is 23, the correlation between pairs is 0.4, a total of 50 evaluable patients achieves a power of at least 90% (calculated power = 91%) for the two-sided test for no difference with a normal distribution and a significance level of 5%.

Fixed Scenario Elements	
Distribution	Normal
Method	Exact
Number of Sides	2
Alpha	0.05
Mean Difference	-12
Standard Deviation	23
Correlation	0.4
Number of Pairs	50
Null Difference	0
Computed Power	0.910

A total of 55 patients should be enrolled in the study to take into account approximately 10% of non-evaluable patients. Estimates of the mean, SD and correlation between pairs are based upon data of previous studies (Laboratoires THEA. Clinical study LT2762-PIV-11/13, 2017) SAS 9.4 was used for the sample size calculation (POWER procedure, PAIRED MEANS statement).

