2.2 Modified intent-to-treat set

The modified intent-to-treat (mITT) set will include all enrolled patients having received at least one dose of the IP and with at least one baseline and post-baseline efficacy assessment. mITT set will be the primary population for the efficacy analysis.

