6.1.2 Sensitivity analysis of the primary efficacy endpoint

Sensitivity analysis will be performed without replacement of missing values on the mITT and PP sets.

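### No planned analysis shows how far the primary VAS result depends on patients who leave because treatment failed: only LOCF and observed cases are planned, and the visit rules can remove the withdrawal value

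*SAP*

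**What the plan says.** The primary analysis is a paired t-test of the D1 to D42 change in VAS on the mITT set (SAP 6.1.1). In that set "missing values will be imputed using the last observation available on treatment method (LOCF" (SAP 4.2). The one alternative is in SAP 6.1.2: "Sensitivity analysis will be performed without replacement of missing values on the mITT and PP sets". SAP Appendix 2 lists matching tables (4.2, 4.3 and 4.6) and no others on missing VAS data. Protocol section 12 adds nothing further.

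Four other provisions bear on this:

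- Protocol 6.6.2.1 lets the investigator withdraw a patient for adverse events, for worsening of dryness, or for "Lack of efficacy: if the patient or the investigator does not feel that the treatment has adequately relieved his/her symptoms".
- SAP 2.2 limits the mITT set to treated patients "with at least one baseline and post-baseline efficacy assessment".
- SAP 4.2 and Protocol 6.6.2.1 ask investigators to try to obtain the D42 evaluations at withdrawal. The flow charts give the last column to D42 or the withdrawal visit and mark the VAS there.
- SAP 4.1 assigns days 1 to 27 to D14 and days 28 to 55 to D42. Within a window it keeps the record closest to the scheduled visit, and it disregards a last visit made more than 24 hours after the last instillation.

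**The concern.** The permitted withdrawal reasons tie missing data to poor outcome. Observed cases leave such a patient out. LOCF replaces the patient's D42 value with an earlier one, which may be better than what D42 would have shown. A treated patient with no efficacy assessment after baseline is in neither analysis.

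The trial is open and single-arm, so the within-patient change is the whole of the primary evidence and no comparison group carries the same error. When failures leave with a good D14 value or with none, both planned analyses err in the same direction, and agreement between them gives little reassurance.

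**Working it through.** **Inputs.** SAP 1.5 states: "Assuming that the mean change is 12, the standard deviation (SD) is 23, the correlation between pairs is 0.4". It also gives 50 evaluable pairs, two-sided 5% and power 0.910, and says: "A total of 55 patients should be enrolled in the study to take into account approximately 10% of non-evaluable patients". The numbers of withdrawals, the failures' changes and the 8 mm scenario below are assumptions. Improvement is a negative change (SAP 4.3.6).

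**The plan's own figure.** SD of change = 23 × √(2 × (1 − 0.4)) = 25.2. Noncentrality = 12 / 25.2 × √50 = 3.37 on 49 df. Exact paired t-test power = 0.910, as stated.

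**Which VAS the rules keep for a patient who withdraws**

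- Visit on days 28 to 55, within 24 hours of the last drop: it counts as D42 and enters both analyses.
- Visit on days 1 to 27, within 24 hours, with no other record in the window: it is available for LOCF and can qualify the patient for mITT.
- Visit on about days 15 to 27 after a D14 visit: both fall in the D14 window, and the D14 record is kept if it is closer to schedule. The SAP does not say whether LOCF uses windowed or raw records.
- Visit more than 24 hours after the last drop: disregarded. The patient contributes D14 or nothing.

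**Effect on the estimate and test.** Take m = 55 − k completers with mean μ and SD 25.2, and k failures all given change x.

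- Mean M = (mμ + kx) / 55.
- SD² = [(m − 1) × 25.2² + m(μ − M)² + k(x − M)²] / 54.
- t = M / (SD / √55) on 54 df.

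Example with k = 5, μ = −12, x = 0: M = (50 × −12 + 0) / 55 = −10.9; SD = 24.3; t = −3.34; p = 0.0015.

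Mean improvement in mm (p-value):

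| Completers improve by | Failures handled as | k = 5 | k = 8 | k = 11 |
|---|---|---|---|---|
| 12 mm | left out (observed cases) | 12.0 (0.0015) | 12.0 (0.0021) | 12.0 (0.0029) |
| 12 mm | no change | 10.9 (0.0015) | 10.3 (0.0022) | 9.6 (0.0031) |
| 12 mm | worse by 10 mm | 10.0 (0.004) | 8.8 (0.010) | 7.6 (0.024) |
| 12 mm | worse by 20 mm | 9.1 (0.011) | 7.3 (0.040) | 5.6 (0.12) |
| 8 mm | left out (observed cases) | 8.0 (0.029) | 8.0 (0.035) | 8.0 (0.041) |
| 8 mm | no change | 7.3 (0.029) | 6.8 (0.035) | 6.4 (0.041) |
| 8 mm | worse by 10 mm | 6.4 (0.060) | 5.4 (0.10) | 4.4 (0.17) |

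LOCF with failures carrying a 6 mm improvement (half the completers' 12 mm) gives 11.5, 11.1 or 10.8 mm.

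**Tipping points.** Solving for the x at which p = 0.05:

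| Completers improve by | k = 5 | k = 8 | k = 11 |
|---|---|---|---|
| 12 mm | +37 mm | +22 mm | +14 mm |
| 8 mm | +7.4 mm | +3.2 mm | +1.2 mm |

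These limits give every failure the same value. Letting failures vary with the same SD adds (k − 1) × 25.2² to the sum of squares and lowers the limits: to about +35, +20 and +12 mm at 12 mm, and to about +4.9, +0.3 and −1.9 mm at 8 mm.

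**The case against.** The best defence is that the plan does try to capture failures. A D42-type evaluation is requested at every withdrawal, and an on-treatment VAS that survives SAP 4.1 enters LOCF and lowers the estimate. On days 28 to 55 it enters observed cases too. This stands. A reader might infer that patients who fail early can never pull the estimate down, or that LOCF always favours the product. The documents do not support either. LOCF is favourable only if the carried value beats the unseen D42 value, and a patient with no benefit at D14 carries no benefit.

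A reader might also infer that counting failures as unchanged could by itself overturn the result. With completers at 8 mm and 11 failures, the mean of 6.4 mm is below 2.005 × 25.2 / √55 = 6.8 mm. But that limit uses the wrong SD. Entering 11 zeros reduces the SD to 22.7 and the limit to 2.005 × 22.7 / √55 = 6.1 mm, so p = 0.041, the same as observed cases. No-change imputation corrects the estimate and hardly tests significance. It also flatters patients who left because they got worse.

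Finally, the study is described as a pilot (Protocol 3.2). With about 10% missing at the design effect, the shift is about 1 to 3 mm and significance holds. That is a fair limit on the size of the problem. It does not answer the 24-hour rule, the closest-record rule or the silence on which record LOCF uses.

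**Conclusion.** The point holds in a conditional form. LOCF and observed cases are the only methods planned for a missing primary VAS. Observed cases favour the product when failures leave. LOCF does so when an earlier, better value is carried, and SAP 4.1 can discard the withdrawal value that would prevent this. No planned output shows how much the result rests on these patients.

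Relative to no change for failures, observed cases overstate the benefit by 1.1, 1.7 or 2.4 mm for 5, 8 or 11 failures among 55 at the design effect. Significance is robust there with about 10% missing. It is fragile if the effect is nearer 8 mm, or if withdrawals are more frequent and failures worsen. All of this rests on the SAP's SD and correlation and on assumed numbers and outcomes of failures. The change should be made, but the primary analysis can stay as it is.

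**What to change.** 1. In SAP 4.1 and 4.2, state that LOCF carries the last raw on-treatment VAS, including the withdrawal-visit value, even when a D14 record shares its window. State that a withdrawal VAS excluded by the 24-hour rule is used in the sensitivity analysis below.
2. In SAP 6.1.2, add a sensitivity analysis on all treated patients with a baseline VAS. Set the D42 change to zero for those who stopped for an adverse event, worsening or lack of efficacy without a usable withdrawal VAS, and for those with no post-baseline VAS. Repeat it over a range of worsening values, for example +10 and +20 mm, and give the tipping point. Report whether the conclusion holds.

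The no-change step alone is not enough, because it leaves the p-value almost where observed cases put it. Protocol 6.6.2.1 already requires the date and primary reason for withdrawal on the CRF, so no new data are needed. The cost is one or two extra tables, an entry in SAP section 8 and a slightly less favourable estimate.

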4.3 Derived and transformed data

Following derived data used for analyses will be calculated.

4.3.1 Baseline

Baseline will be defined for each assessment as an evaluation before the first instillation of the IP.

- For FBCVA, value recorded at Screening visit will be the baseline
- For others parameters, value recorded at Day 1, will be the baseline

Baseline value will be the one in the concerned eye for endpoints assessed/analysed by eye.

4.3.2 Age (years)

Age (years) will be calculated in classes as: Age < 65 vs Age ≥ 65.

4.3.3 Time since Dry Eye Disease (DED) diagnosis

Time since Dry Eye Disease (DED) diagnosis (months) will be calculated as:
(Date of screening Visit [D-14/D-10] – Date of diagnosis) / 365.25 x 12.

If the day is missing and month is present the 15 of the month will be used. If year is present and day and month are missing, the time since DED diagnosis will be calculated as (Year of screening visit [D-14/D-10] – Year of diagnosis) x 12.

4.3.4 Duration of treatment

Duration of physiol (days) will be calculated as (Date of last instillation – Date of first instillation) + 1.

Duration of IP (days) will be calculated as (Date of last instillation at D42 or premature discontinuation visit – Date of first instillation at D1) + 1.

If the day or the month is missing for one of the dates, the duration of treatment (physiol or IP) will be missing.

4.3.5 Mean dose regimen (instillations / day)

The mean dose regimen (instillations / day) will be calculated in classes as:
Mean dose regimen \leq 4 vs Mean dose regimen $>$ 4.

4.3.6 Change from baseline

Change from baseline will be calculated as the difference:
Assessment at the visit – Assessment at baseline.

4.3.7 Change from baseline in classes

Change from baseline in classes will be defined as detailed below:

In four classes:

- Improvement (Decrease of score from baseline): Change from baseline $<$ 0
- Absence stable: Change from baseline = 0 and absence of symptoms
- Presence stable: Change from baseline = 0 and presence of symptoms
- Worsening (Increase of score from baseline): Change from baseline $>$ 0

In three classes compared to 0:

- Improvement (Decrease of score from baseline): Change from baseline $<$ 0
- No change: Change from baseline = 0
- Worsening (Increase of score from baseline): Change from baseline $>$ 0

In three classes compared to -1/1:

- Improvement of more than 1 point: Change from baseline $<$ -1
- No change: Change from baseline \geq -1 and \leq 1
- Worsening of more than 1 point: Change from baseline $>$ 1

4.3.8 Symptomatology evaluation (mm)

The Symptomatology evaluation (on VAS) will be calculated as follows:
[VAS Score (mm) / Scale length (mm) x 100].

4.3.9 Global ocular staining

The Global ocular staining assessed using a 15-point scale (grades of 0–5) will be calculated by adding the individual scores of the three zones (Temporal bulbar conjunctiva, corneal area, nasal bulbar conjunctiva). If any individual score is missing, so will be the global score.

4.3.10 Van Bijsterveld score

The corneo-conjunctival exposed surface is separated in three parts: nasal bulbar conjunctive, corneal area, and temporal bulbar conjunctive. The following score will be attributed to each of these parts with the help of a visual figure representing each degree of staining:

- (0) = No coloration
- (1) = Some punctuations.
- (2) = Well defined punctuations.
- (3) = Total coloration.

The Van Bijsterveld score is the addition of the scores obtained in the three parts (nasal, corneal and temporal). If any individual score is missing, so will be the Van Bijsterveld score.

4.3.11 Ocular Surface Disease Index (OSDI)

The OSDI score will be calculated as follows:

[Sum of the scores for all questions answered x 25] / [(total number of questions answered)].

The OSDI score will be also calculated in classes:

- None: ≥ 0 and <13 ; Mild: ≥ 13 and <23 ; Moderate: ≥ 23 and <33 ; Severe: ≥ 33 and ≤ 100 ;
- <18 vs ≥ 18 .

4.3.12 Total score of ocular symptoms

The following dry eye symptoms have been assessed for both eyes (globally) and collected using a 4-point ordinal scale (0 = absent to 3 = severe, very distressing and interfering with daily activities):

- burning/irritation,
- stinging/eye pain,
- ichting/pruritus,
- eye dryness feeling,
- foreign body sensation,
- tearing,
- light sensitivity.

The total score of ocular symptoms (ranging from 0 to 21) will be calculated by adding the individual scores of the seven symptom scores, higher score representing greater distress. If any symptom is missing, so will be the total score.

4.3.13 Schirmer score

Schirmer score will be calculated in classes as:

<5 , ≥ 5 and <10 and ≥ 10 mm/5 minutes.

4.3.14 Tear Break-Up Time (TBUT)

TBUT mean (seconds) will be calculated as:

Mean of (1st measure, 2nd measure, 3rd measure).

If only one measure is recorded, this single measure will be used for assessment of the mean.

The TBUT score will be also derived in classes: <5 , ≥ 5 and ≤ 10 and >10 seconds.

4.3.15 Ocular symptoms upon instillation

Duration of ocular symptoms upon instillation:

If seconds are missing and minutes are present, the seconds are 0.

If minutes is missing and hours are present, the minutes and seconds are 0.

Total score of ocular symptoms upon instillation:

The total score of ocular symptoms upon instillation (ranging from 0 to 15) will be calculated by adding the individual scores of the five symptoms scores: burning/irritation, stinging/eye pain, itching/pruritus, eye dryness feeling, foreign body sensation. If any individual score is missing, so will be the total score.

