9.1.4 Ocular symptoms upon instillation

Ask the patient:

“Have you felt any ocular discomfort/unusual sensation UPON INSTILLATION since the last visit?”

« Avez-vous ressenti une gêne/sensation oculaire inhabituelle à l'instillation depuis la dernière visite ?» If the answer is yes, a table regrouping the functional ocular signs will have to be completed.

burning/irritation, stinging/eye pain, itching/pruritus, eye dryness feeling, foreign body sensation, and other symptoms will be graded by the patient.

according to the following severity scale and with their duration:

(0) = Absent.

(1) = Mild: present but not disturbing.

(2) = Moderate: disturbing, but not limiting with daily activities.

(3) = Severe: Very distressing and interfering with daily activities.

The ocular symptoms upon instillation will be assessed in global for both eyes at each visit post-baseline.

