11 DATA MANAGEMENT

11.1 Procedures used for data review, database cleaning and issuing/resolving data queries

11.1.1 Data entry

The personnel in charge of the study in the centres will record data to paper case report form.

A data entry mask will be created/performed as well as instructions for the data entry.

A double independent data entry will be done from the case report forms by the designed technician(s) or operator(s). The double data entry will be checked by comparison of both entries. A final quality control will be done on a part of the CRFs ($\sqrt{n+1}$).

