7.1 Ocular symptoms upon instillation

Ocular symptoms upon instillation (burning/irritation, stinging/eye pain, itching/pruritus, eye dryness feeling, foreign body sensation) are assessed using a 4-point ordinal scale from 0 to 3, 0 indicating no symptom and 3 indicating very disturbing symptoms.

Frequency distribution of each symptom will be presented at each assessment time (D14 and D42).

The duration (minutes) and the frequency will be described by symptom on the subgroup of patients presenting with the symptom (i.e. with severity ≥ 1).

The total score of the five symptoms, ranging from 0 to 15, will be calculated and presented for D14 and D42.

Data relative to other symptoms will be provided in an individual patient data listing. Other symptoms will be coded using MedDRA 21.1, September 2018 (English).

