9 VALIDATION OF STATISTICAL PROGRAMMING

Validation of statistical programming will be performed in agreement with Aixial SOP.

Logs of all programs used for analysis and data preparation will be checked for errors and unexpected warnings.

Double programming of worse/contralateral eye, derivation and analyses regarding primary endpoint will be performed by the lead statistician. Else, a third party will review all statistical outputs (tables, figures) and results from statistical tests/models, as well as SAS code of all statistical programs. This includes programs used to derive data and macros developed for the study.

Any undocumented updating of study data in statistical programs instead of change in clinical database (or source data) is not allowed. Specifically, this refers to the cases where subjects or the data are added/changed using a statistical program rather than updating the database. This kind of hard coding is usually proposed to correct deficiencies (missing values, wrong values, and wrong measurement units) in the database when these errors are detected after database lock.

No hard coding is done in any programs used for the creation of analysis data sets, tables, listings, or analyses that are intended for external reporting after database lock (i.e. clinical study reports, publications, abstracts, etc.). For particular cases, a footnote will be added in the corresponding table.

This policy ensures integrity of clinical data, since no changes are made to the study data without appropriate documentation from the investigator sites and appropriate audit trails within the clinical trial database.

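### Must the SAP state that a No to the instillation question counts as grade 0 before the five grades and the 0–15 total can be analysed?

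*SAP*

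**What the plan says.** Protocol 9.1.4 has two steps. The patient is asked a yes/no question about discomfort or unusual sensation since the last visit. Then: "If the answer is yes, a table regrouping the functional ocular signs will have to be completed". Each symptom in the table is graded 0 to 3, with 0 meaning absent. The same section adds: "The ocular symptoms upon instillation will be assessed in global for both eyes at each visit post-baseline". Protocol 11.1.1 says how the data are captured: "The personnel in charge of the study in the centres will record data to paper case report form".

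SAP 4.3.15 has two parts. The first completes partly recorded durations, for example: "If minutes is missing and hours are present, the minutes and seconds are 0". The second defines the total as the sum of five symptom grades, from 0 to 15, with one rule for blanks: "If any individual score is missing, so will be the total score".

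SAP 7.1 plans the frequency distribution of each symptom and the total at D14 and D42. Only duration and frequency are restricted; they "will be described by symptom on the subgroup of patients presenting with the symptom", meaning severity of at least 1. Section 7 places all of this on the Safety set. SAP section 3 leaves missing values out of percentages. The last-observation rule in SAP 4.2 is stated for the mITT set, so it does not reach these safety tables.

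**The concern.** Put together, these sections allow an unwelcome literal reading. After a No, nobody is told to write a grade. On a paper form the five fields may stay empty. Empty fields are missing, missing grades leave the percentages, and any missing grade makes the total missing. Tables 5.1 to 5.6 would then describe only patients who answered Yes. Symptom percentages would be too high, grade 0 percentages too low, and a true No could not be told apart from a question never asked.

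This would matter to a reader, because Protocol 3.4 names short-lived burning or stinging when the drop goes in as an expected risk, and these tables measure it most directly. The total is also an SAP addition (section 8), so the protocol offers no derivation to fall back on.

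Two further points seemed to add weight. The SAP has a rule for blank duration fields but none for blank grades after a No. And SAP section 9 is strict about programs that alter data: "Any undocumented updating of study data in statistical programs instead of change in clinical database (or source data) is not allowed", with missing values among its examples: "This kind of hard coding is usually proposed to correct deficiencies (missing values, wrong values, and wrong measurement units) in the database". A programmer might hesitate to turn blanks into zeros without a written rule.

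**Working it through.** **The plan's own figure.** Five symptoms graded 0 to 3 give a total from 5 × 0 = 0 to 5 × 3 = 15. This agrees with SAP 4.3.15.

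**Size under the adverse reading.** Let N be the patients assessed, Y those answering Yes, and x those with grade 1 or more on one symptom. If a No is missing, the table shows x/Y; if a No is 0, it shows x/N. The ratio is N/Y, provided every Yes patient grades the item. N = 55 is the planned enrolment (SAP 1.5), used here as if all were assessed. Y and x are assumptions, since the documents give no values. Intervals use the Wilson formula of SAP section 3 with z = 1.96.

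| Y | x | No = missing: x/Y (95% CI) | No = 0: x/55 (95% CI) | Ratio 55/Y |
|---|---|---|---|---|
| 5 | 4 | 80.0% (37.6–96.4) | 7.3% (2.9–17.3) | 11 |
| 11 | 8 | 72.7% (43.4–90.3) | 14.5% (7.6–26.2) | 5 |
| 20 | 15 | 75.0% (53.1–88.8) | 27.3% (17.3–40.2) | 2.75 |
| 40 | 30 | 75.0% (59.8–85.8) | 54.5% (41.5–67.0) | 1.38 |
| 55 | 41 | 74.5% | 74.5% | 1 |

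One interval worked through, for 8/11: 2np = 16, z² = 3.8416, 4npq = 4 × 8 × 3/11 = 8.727. The root term is 1.96 × √(3.8416 + 8.727) = 6.949 and the denominator is 2 × (11 + 3.8416) = 29.683. The limits are (19.842 − 6.949)/29.683 = 43.4% and (19.842 + 6.949)/29.683 = 90.3%.

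For the total, assume 11 Yes patients, each with a true total of 3. If a No is missing, the mean is 33/11 = 3.0; if a No is 0, it is 33/55 = 0.60.

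The opposite error is possible if a No is 0 but items left blank after a Yes stay missing. If 0, 4, 8 or 11 of the 11 leave an item blank, the mean total is 33/55 = 0.60, 21/51 = 0.41, 9/47 = 0.19 or 0/44 = 0.00.

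**Which reading the text supports.**

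- Grade 0 is defined as absence, and a No says that nothing was felt. The two carry the same information.
- Protocol 9.1.4 treats these symptoms as assessed at each post-baseline visit, not only in patients with complaints.
- SAP 7.1 restricts duration and frequency to patients with the symptom and places no restriction on the grades or the total. On its own this is supportive, not decisive, because a Yes patient can also have grade 0 on an item.
- The total starts at 0. This too is only supportive, since a Yes patient whose sole complaint is outside the five listed symptoms could score 0.

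Together they point one way. Nothing in either document suggests that the tables are meant for Yes patients only.

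**Blanks after a Yes.** Protocol 9.1.4 requires the table to be completed, so a blank is a data error. Protocol 11.1.2 provides consistency checks and data clarification forms, and 11.1.4 locks the database once queries are resolved. For anything still blank, SAP 4.3.15 already makes the total missing. The sequence ending in 0.00 needs every Yes patient to leave a required item blank and every query to fail.

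**Durations.** The rules fill seconds only where minutes are recorded, and minutes and seconds only where hours are recorded. A wholly blank duration is not set to 0. They complete a partly entered time and set no precedent for blank grades.

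**SAP section 9.** It bars undocumented changes to data and is aimed at errors found after database lock. A recorded No is not a deficiency in the data. Deriving 0 from it is an ordinary derivation, and section 9 itself provides for review of the programs that derive data.

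**The case for a change.** The best argument for acting is that the missing-item rule was carried over from a setting where it fits. The seven-symptom total in SAP 4.3.12 uses the same rule, but there every symptom is asked directly (Protocol 8.1.2.7). Here an opening question stands in front of the grades, and the rule takes no account of it. The SAP does write down comparable conventions elsewhere, such as a single TBUT reading (4.3.14) or a missing causality assessment counted as related (7.5.1). A sentence here would cost almost nothing.

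Part of this stands. No sentence says that a No is 0, and the literal chain from blank to missing to excluded can be followed through the text. What does not stand is the step from an unwritten convention to a wrong result. That step needs the form or database to hold blanks after a No, and it needs an analyst to treat a recorded answer as uncollected. How a No is stored is a matter for CRF version 1.0, cited in the SAP introduction but not among the documents here, and for the annotated CRF and data validation plan foreseen in Protocol 11.1.2. Even if both things happened, the table shell in SAP Appendix 3 prints n and the number missing, so a sharp drop in n would show at once.

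**Conclusion.** No change to the plan is called for. This is a derivation detail that an analyst fills sensibly: a recorded No is grade 0 on the five symptoms and 0 on the total, and an unanswered opening question is missing. With that coding, or if the CRF already stores zeros, no result changes.

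Under the other reading, symptom percentages would be multiplied by assessed patients over Yes patients, which is 1 to 11 for 55 down to 5 Yes among 55. Those counts are assumptions, and the documents do not allow the factor to be estimated. The tables affected are descriptive safety summaries in a single-arm, open-label pilot. Adverse events and tolerance ratings are reported separately, and the efficacy analyses and sample size do not depend on these grades.

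The conclusion rests on two assumptions: that the answer to the opening question is itself recorded, and that the programmer follows the meaning of grade 0 given in Protocol 9.1.4.
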